7.5 Description and justification of route of administration and dosage

The vaccination will be administered by a 1 ml intramuscular injection, delivering 20 microgram of hepatitis B antigen. This is the standard injection dose (Engerix-B 20 microgram/1 ml, suspensie voor injectie | Geneesmiddeleninformatiebank | College ter Beoordeling van Geneesmiddelen).

7.6 Dosages, dose modifications and method of administration

Vaccinations will be given according to an accelerated schedule, on days 57, 71 and 85 (all +/- 1 day) of the study (day 1 being the date of V2). Here an accelerated schedule is used to provide a suboptimal trigger to the immune system, reasoning that this will be more reflective of natural infections and will leave room for improvement of the response due to the supplementation with Lacprodan® OPN-10. At the end of the study, the anti-HepB titer will be assessed, and the vaccination coverage will be known. Subjects with an insufficient coverage will be informed that for full coverage a fourth vaccination can be obtained 12 months after the first vaccination, through the study team.

7.7 Preparation and labelling of Non Investigational Medicinal Product

The vaccine must be stored at a temperature of $2^{\circ}C - 8^{\circ}C$ (not in the freezer). Before use, the vaccine must be shaken, after which it will get somewhat cloudy. A visual check must be done on strange particles or an abnormal appearance. After opening of the package, the vaccine must be administered immediately.

7.8 Non-investigational product accountability

The vaccine will be ordered from the pharmacy and stored in a locked box until use under the prescribed conditions (refrigerator, 2-8°C). Only the medical investigator and the study coordinator

will have access to the box. If any material is left after completion of the study, this will be returned to the pharmacy.

8 METHODS

8.1 Study parameters/endpoints

Details of sample handling and analytical methods will be described in a separate Lab Manual, to be completed before study start.

8.1.1 Main study parameter/endpoint

Primary outcome is the percentage of responders to hepatitis B vaccination. A "responder" is defined as a subject attaining anti-hepatitis B antibody titres >10 IU/L at Visit 7 (2 weeks after the third vaccination). Antibody titres will be determined with ELISA.

8.1.2 Secondary study parameters/endpoints

- Change in serum anti-hepatitis B antibody titres from baseline (V1) to 14 days after the second vaccination (V6) and 14 days after the third vaccination (V7)
- Change in circulating cytokines from baseline to 8 weeks intervention (V4) and to the end of the study (V7). The analyses will be performed at NIZO with a multiplex assay in duplicate. Results will be displayed in pg/ml (dependent on the actual outcomes). In principle, the following set of cytokines will be analysed; however, the final choice of the most relevant cytokines may be slightly different, depending on the outcomes of ongoing analytical validation experiments.
 - Interleukin 6 (IL-6)
 - Interleukin 10 (IL-10)
 - Interferon y (IFNy)
 - Tumour necrosis factor α (TNFα)
 - Chemokine (C-C motif) ligand 3 (CCL-3)
 - Interleukin 15 (IL-15)
 - Interleukin 17a (IL-17a)
 - Interleukin 4 (IL-4)
 - Interleukin 2 (IL-2)
 - Interleukin 2RA (IL-2RA)
- Change in serum levels of P1NP and CTX-1 (as markers of bone formation and bone resorption) from baseline to 8 weeks intervention. Analyses will be performed by an external routine lab.
- Change in plasma levels of hOPN and bOPN from baseline to 4 weeks and 8 weeks intervention. hOPN and bOPN will be analysed at NIZO with an ELISA assay in duplicate. Results will be displayed in pg/ml (dependent on the actual outcomes).

NL81499.028.22 BOFEI

• Change in serum LPS binding protein (LBP) from baseline to 8 weeks intervention. Serum LBP will be analysed at NIZO with an ELISA assay in duplicate.

- Incidence of self-reported URTI or LRTI during the trial, including weekly reports of symptoms related to upper and lower respiratory tract infections
- Safety monitoring by routine assays for hematology and serum clinical chemistry. Analyses will be performed by an external routine lab.

Table 4 Blood parameters for safety monitoring:

Clinical chemistry	Method	Unit
Serum alkaline phosphatase	Photometry	U/I
Serum alanine aminotransferase (ALAT)	Photometry	U/I
Serum aspartate aminotransferase (ASAT)	Photometry	U/I
Serum triacylglycerols	Photometry	mg/dl
Serum total cholesterol	Photometry	mg/dl
Serum total bilirubin	Photometry	mg/dl
Serum urea	Photometry	mg/dl
Serum Creatinine	Photometry	mg/dl
Serum hs C-reactive protein	Nephelometry	mg/dl
Serum albumin	Nephelometry	mg/dl
Blood Glucose (Sodium Fluoride tubes, NaF)	Photometry	mg/dl
Hematology		
Red blood cell (RBC) count	Flow cytometry	10^12/L
White blood cell (WBC) count	Flow cytometry	10^9/L
Hemoglobin	Photometry	g/L
Hematocrit	Photometry	L/L
Platelet	Flow cytometry	10^9/L
Differential leukocyte count	Flow cytometry	%

8.1.3 Other study parameters (exploratory)

- Change in plasma brain-derived neurotrophic factor (BDNF) from baseline to 8 weeks intervention (optional)
- Change in faecal microbiota composition after 8 and 14 weeks intervention (analysis depending on results for primary and secondary outcomes)

8.2 Randomisation, blinding and treatment allocation

To ensure blinding of the NIZO study team, an independent person in the AFI study team will be responsible for assigning a random 5-digit number code to the products. The number code is printed on the label of each carton box. Per treatment 3 different, 5 digits, codes will be used. The NIZO and EBMR teams, laboratory personnel and participants will be unaware of the coding until all data analyses are finished and until after the blind data review meeting. Only in a case of emergency possibly related to treatment, the Principal Investigator can request the independent party to open a sealed de-blinding envelope containing information to check the type of treatment of (a) particular subject(s) without disclosure of the other treatments.

Allocation will be stratified for gender and age.

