4.4 Sample size calculation

Sample size calculation was based on a publication by Albers et al. (Albers et al. 2003). In this study (with another nutritional intervention), seroconversion after hepatitis B vaccination in the placebo group was 33%, and it was 63% in the active group. For the present study, we assumed seroconversion of 25% in the placebo group. To be able to detect a doubling of seroconversion (to 50%) in the active group, a sample size of 58 subjects per group was calculated (Sample Size Calculator (clincalc.com)), with an alpha of 0.05 and a power of 0.8. Taking into account a drop-out rate of ~15%, we propose to include 70 subjects per group.

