6.7 Preparation and labelling of Investigational Product

Test and placebo products will be delivered to NIZO separately by the sponsor and will be stored at the recommended conditions.

On the label of the bulk package, the following information will be provided by the sponsor: Bulk packaging coming from sponsor

- Company name sponsor
- Project number of the study (xxx)
- Manufacturing batch number
- Number of carton boxes with 30 sachets
- Expiry date
- The text "for nutrition trial use only"

An example of the label of the bulk package is included in section D3 of this submission.

The products will be packaged in carton boxes. All boxes will contain 30 sachets. The sachets will be marked with one dot (.) for the sachets with a level of 1,25g/sachet and with two dots (..) for the sachets with a level of 1,6 g/sachet. Each carton box will be delivered to NIZO with the following information:

- Best before [date]
- Random 5-digit code (see section 8.2)
- Number of sachets

NIZO will add an additional label to the carton boxes with the following:

- Study name
- Subject number
- "To be used in study weeks: ..."
- The text "for nutrition trial use only" (in Dutch)

For the active treatment, 3 random 5-digit codes will be used; for the placebo treatment, 3 other random 5-digit codes will be used. Each carton box will be coded with one of the three applicable codes.

For each subject, 2-weekly packages will be prepared by NIZO. Labelling of these packages with the individual subject codes and weeks will be performed by NIZO. After arrival of the bulk package at NIZO, the NIZO study team will be responsible for labelling of the 2-weekly doses of the study products.

The label that will be used on the 2-weekly package for the subjects ('Voorbeeldetiket D3') will contain the following information:

- Study name and project number
- Subject number
- Best before [date]
- Random 5-digit code (see section 8.2)
- The text "for nutrition trial use only" (in Dutch)
- Information for use
- Information about storage conditions
- Contact details of the researcher

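### With three shared codes per arm on the labels, one emergency unblinding can reveal the arm of about 22 other subjects

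*Protocol*

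**What the plan says.** Protocol section 6.7 sets the coding: "For the active treatment, 3 random 5-digit codes will be used; for the placebo treatment, 3 other random 5-digit codes will be used". It adds: "Each carton box will be coded with one of the three applicable codes". Section 8.2 repeats the number of codes, "Per treatment 3 different, 5 digits, codes will be used", and says where they appear: "The number code is printed on the label of each carton box". The list of label items in section 6.7 puts the same type of 5-digit code on the 2-weekly package, together with the subject number.

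The link between subject and code is made by a team that is meant to stay blinded: "Labelling of these packages with the individual subject codes and weeks will be performed by NIZO". Under section 6.8 the other blinded team, EB Medical Research, hands out the boxes at visits 2 to 6, takes them back at visits 3 to 7 and counts the leftover sachets.

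Section 8.2 keeps both teams, the laboratory and the participants blinded until the data analyses and the blind data review are complete. It allows one exception: in an emergency possibly related to treatment, the Principal Investigator may ask an independent party to open an envelope showing the treatment of "particular subject(s) without disclosure of the other treatments". The protocol describes no kit number unique to a subject, and it does not say whether a subject keeps one code throughout.

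**The concern.** An envelope can be specific to one subject, but these labels are not. Each code belongs to one arm only and is shared by many subjects, so the arm of one subject is also the arm of everyone with that code. The people who would learn the result of an emergency unblinding work with, or belong to, teams that see the codes and subject numbers side by side.

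What is at stake is the handling of the remaining subjects. Adverse events are recorded when subjects report them spontaneously or staff observe them (section 9.2.1). The medical investigator may stop individual participation (section 13.1, item j), and withdrawn subjects are generally not followed up (section 8.6), so a withdrawal can also cost a visit 7 titre. Per-protocol exclusions are applied at a data review that is supposed to be blind (section 10). Each of these steps involves judgement that knowledge of the arm could influence.

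**Working it through.** **Inputs**
- Subjects per arm: 70, so 140 in total (section 4.4: "Taking into account a drop-out rate of ~15%, we propose to include 70 subjects per group").
- Codes per arm: 3, none shared between arms (sections 6.7 and 8.2).
- Minimum number of completers: 105 (section 8.5).
- Sachets: 30 per box (section 6.7), 2 per day (section 6.6).
- Supply: 4 weeks at visits 2 and 3, and 2 weeks at visits 4, 5 and 6 (section 8.3.3).

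**The plan's own figure.** For 25% versus 50%, two-sided alpha 0.05 and power 0.80, the usual two-proportion formula with pooled variance and no continuity correction gives 58 per group, as stated. Allowing for 15% drop-out, 58/0.85 = 68.2, or 69; the protocol rounds to 70. The sample size is not in dispute and only supplies the 70 per arm.

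**One code per subject, codes used equally (both assumed)**
- Subjects per code: 70/3 = 23.3, including the unblinded subject.
- Others revealed: 23.3 − 1 = 22.3, and 22.3/139 = 16%.
- Among 105 completers: 52.5/3 = 17.5 per code, so 16.5 others, and 16.5/104 = 16%.
- If the codes are used unequally, with n1 + n2 + n3 = 70, the average group size for a randomly chosen subject is (n1² + n2² + n3²)/70. This is never below 70/3, so 22 is the low end on average.

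**More than one code per subject (permitted by the per-box wording, not stated)**
- Boxes per subject: 56 sachets for each 4-week period need 2 boxes, and 28 sachets for each 2-week period need 1. The total is 2 + 2 + 1 + 1 + 1 = 7.
- Two codes of the arm exposed, with each of the other subjects carrying one code: 2 × 70/3 − 1 = 45.7, so about 46 others.
- All three exposed: the other three codes follow by elimination, so all 139 others are revealed.
- If, as a further assumption, every box code were drawn at random, the chance that a subject holds all three codes is 1 − 3(2/3)^7 + 3(1/3)^7 = 83%. For exactly two codes it is 17%, and for one code 3(1/3)^7 = 0.1%.

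**With a unique number per subject or box.** The label reveals no other subject.

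**The case against.** The envelope itself can be confined to one subject, and an independent party opens it only in an emergency. The leak is an inference that also requires the subject-to-code link. The protocol describes the risks of participation as small, and nothing in it allows the probability of an unblinding to be estimated. Three codes per arm also give more protection than a single code per arm would. All of this stands, and it limits how often the weakness would matter. It does not make the promise in section 8.2 true, because the blinded teams hold the link as part of routine work.

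The route to bias is also narrow. The primary endpoint is an ELISA titre against a fixed cut-off, measured by blinded laboratory staff, and most secondary outcomes are laboratory assays too. Respiratory symptoms are entered online by the subjects, who have no stated access to other subjects' codes. Compliance is a sachet count. These points stand as well.

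A reader might infer three stronger things, none of which the document supports:
- **One unblinding exposes the whole trial.** This needs a subject's boxes to carry all three codes of the arm. The per-box wording allows it, but the single code listed on the 2-weekly package label fits one code per subject at least as well. The 83% above depends on random drawing of box codes, which the protocol does not describe.
- **Staff could work out the arms from symptoms clustering by code, without any unblinding.** This is conjecture; the protocol gives nothing from which to judge it.
- **The primary result is compromised.** No mechanism is apparent by which a box code would change a titre, apart from the indirect effect of withdrawals on missing visit 7 samples.

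**Conclusion.** The point holds as a conflict within the protocol: the labelling in sections 6.7 and 8.2 defeats the single-subject unblinding that section 8.2 promises. One emergency unblinding lets anyone with the subject-to-code link infer the arm of about 22 other subjects, 16% of the rest, given equal use of the codes and one code per subject. The number is larger if a subject's boxes carry more than one code, which the protocol leaves open. This size is conditional on an unblinding taking place, and the probability of that is unknown. The consequences fall mainly on adverse event recording, withdrawal decisions and per-protocol judgements, and little on the ELISA titre. It is worth correcting before the product is packed, because a statistical analysis plan cannot repair a labelling scheme.

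**What to change.** In sections 6.7 and 8.2, replace the six shared codes on all site-facing and subject-facing labels by a unique random kit number per subject, or per box. Let only the independent code holder keep the list that links kit numbers to arms. Keep any shared product or batch code that would identify the arm off those labels. The blinded packing team then needs only a list showing which kit number goes to which subject. With this change the emergency unblinding statement in section 8.2 can stay as written.

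The cost is a kit list that respects the two weight bands, which are known only from screening, together with label printing and some spare kits. Numbering per box means about 140 × 7 = 980 numbers. Numbering per subject needs only 140 plus spares. Every box already receives a subject-specific label, so no new handling step is needed.

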8.3 Study procedures

8.3.1 Recruitment

Candidates from the Netherlands will be recruited by Link2Trials B.V. (Haarlem) with support of EB Medical Research. Subjects will be recruited by advertisements in regional newspapers and on social media, and, if needed, by advertisements in local newspapers and by posters mounted in public buildings. Candidate matching the main in and exclusion criteria as indicated during recruitment, will be contacted for a registration call after which they will receive information of the study. Candidates will be invited for an information meeting or online meeting (via Teams) with the medical investigator or one of the delegated research team members. The medical investigator or team member will explain the background, objectives and study procedures. During this meeting, subjects have the possibility to ask questions about the study. When candidates indicate to be interested in participation they are invited to sign the informed consent form. After the consent form has been signed, a health questionnaire will be distributed and the subjects will be asked to complete the questionnaire. Subjects who are willing to participate and are considered to be healthy as assessed by the medical investigator on the basis of the health questionnaire, will be invited for the screening visit.

8.3.2 Screening visit (visit 1)

All study visits are scheduled to take place at NIZO, [name] in Ede or at EB Medical research, [name] in Almere.

The subjects will have a pre-study screening (V1) within 2-4 weeks before visit 2, the start of the intervention period.

During the screening visit, a blood sample will be drawn, for the determination of anti-hepatitis B antibody titer, and for a routine safety panel (clinical chemistry and hematology, as listed under 8.1.2). Body weight and height will be measured. A subject's eligibility will be assessed based on the

lifestyle and health questionnaire, BMI, antibody titer, clinical chemistry and hematology. The medical investigator will inform the subjects about their eligibility in writing. In case of a surplus of eligible participants, random allocation will determine which of these participants will be able to join the study.

During the screening visit, verbal instructions will be provided about the collection of fecal samples. All screened subjects will receive a fecal collection kit before visit 2. This kit will also contain written instructions about the collection of fecal samples.

8.3.3 Study Visits

Visit 2

After the screening visit and assessment of eligibility, subjects will be invited for the baseline visit (visit 2, week 0). All subjects will be asked to collect a fecal sample on the day before the visit (with a maximum time window of 48 hours before the visit). Furthermore, all subjects are asked to not eat or drink anything, except water after 21:00 on the day before the visit, to not consume alcoholic beverages on the day before the visit, and to not perform intense physical exercise. After arrival in fasted state,

- Overall wellbeing will be checked, including questions on common infectious diseases
- Compliance with study restrictions will be checked
- Fecal samples, collected at home and brought to the site by the participant, will be taken in
- Fasting blood samples will be drawn (before 12 a.m.) see sampling schedule in section 8.3.4
- Test products will be handed out for a 4-week period (until V3).

The duration of visit 2 will be about 30 minutes for each subject.

Visit 3

All subjects are asked to not eat or drink anything, except water after 21:00 on the day before the visit, to not consume alcoholic beverages on the day before the visit, and to not perform intense physical exercise. After arrival in fasted state,

- Overall wellbeing will be checked, including questions on common infectious diseases
- Compliance with study restrictions will be checked
- Fasting blood samples will be drawn (before 12 a.m.) see sampling schedule in section 8.3.4
- Test products will be handed out for a 4-week period (until V4).
- A fecal collection kit will be handed out for fecal collection the day before V4.

The duration of visit 3 will be about 20-30 minutes for each subject.

Visit 4

All subjects are asked to not eat or drink anything, except water after 21:00 on the day before the visit, to not consume alcoholic beverages on the day before the visit, and to not perform intense physical exercise. After arrival in fasted state,

- Overall wellbeing will be checked, including questions on common infectious diseases
- Compliance with study restrictions will be checked
- Fecal samples, collected at home and brought to the site by the participant, will be taken in
- Fasting blood samples will be drawn (before 12 a.m.) see sampling schedule in section 8.3.4
- After blood collection, the hepatitis B vaccine will be administered by intramuscular injection
- Test products will be handed out for a 2-week period (until V5).

The duration of visit 4 will be about 30-45 minutes for each subject.

Visit 5

All subjects are asked to not consume alcoholic beverages on the day before the visit, and to not perform intense physical exercise. After arrival in the morning,

- Overall wellbeing will be checked, including questions on common infectious diseases
- Compliance with study restrictions will be checked
- The hepatitis B vaccine will be administered by intramuscular injection
- Test products will be handed out for a 2-week period (until V6).

The duration of visit 5 will be about 20-30 minutes for each subject.

Visit 6

All subjects are asked to not eat or drink anything, except water after 21:00 on the day before the visit, to not consume alcoholic beverages on the day before the visit, and to not perform intense physical exercise. After arrival in fasted state,

- Overall wellbeing will be checked, including questions on common infectious diseases
- Compliance with study restrictions will be checked
- Fasting blood samples will be drawn (before 12 a.m.) see sampling schedule in section 8.3.4
- After blood collection, the hepatitis B vaccine will be administered by intramuscular injection
- Test products will be handed out for a 2-week period (until V7).
- A fecal collection kit will be handed out for fecal collection the day before V7.

The duration of visit 6 will be about 30-45 minutes for each subject.

Visit 7

All subjects are asked to not eat or drink anything, except water after 21:00 on the day before the visit, to not consume alcoholic beverages on the day before the visit, and to not perform intense physical excercise. After arrival in fasted state,

- Overall wellbeing will be checked, including questions on common infectious diseases
- Compliance with study restrictions will be checked
- Fecal samples, collected at home and brought to the site by the participant, will be taken in
- Fasting blood samples will be drawn (before 12 a.m.) see sampling schedule in section 8.3.4

The duration of visit 7 will be about 20-30 minutes for each subject.

